C									

CONFIDENTIAL

Print date: 2022-10-27 21:48

	Title 05DF2209, Clinical Study Protocol R Lyft Jawline CA	Do N	^{sc id} /IA-52559	
¹ Prior to any planned treatment ² Omitted if the screening and baseline visits occur on Day 1. Screening visit and baseline visit can be combined if no drug washout is needed ³ For females of childbearing potential ⁴ Visit is scheduled only if initial treatment or optional touch-up has been performed ⁵ Omitted if optional touch-up is not performed ⁶ For assessing subject treatment needs only ⁷ Time for returning to social engagements asked to the Subject over the phone ⁸ Beview diary with Subject over phone			AE = Adverse event $EOS = End of Study$ $GAIS = Global Aesthetic In$ $hrs = hours$ $TC = Telephone call$ $TU = Touch-up$ $Tx = Treatment$	nprovement Scale

Table 2 Schedule of events – No Treatment group

Procedure	Visit 1	Visit 2	Visit 3	Visit 4-6	Visit 7	Visit 7a ³
	Day -21 to Day 1	Day 1	1 month after baseline (+7 days)	3, 6 and 9 months after baseline (±14 days)	12 months after baseline (±14 days)	2 weeks after optional Tx (±7 days)
	Screening	Baseline	Follow-up	Follow-up	Follow-up/ Optional Tx/ EOS	Follow-up/ EOS
Informed Consent	Х					
Med. Hx/prior therapies	Х	X ¹				
Demographics	Х					
Height/Weight ⁶		Х			Х	
Inclusion/Exclusion Criteria	Х	X^1			X ^{4,5}	
Urine pregnancy test ²	Х	X^1			X ^{4,5}	
Randomization		Х				
Treatment with study product					X ⁴	
Evaluate device deficiencies					X ⁴	
Photography		Х	Х	Х	X ⁵	
Concomitant therapies	Х	X^1	Х	Х	Х	Х
Assessment of AEs		Х	Х	Х	Х	Х
Treating Investigator Assessments						
GAIS				X	Х	X
Galderma Jawline Scale ⁷	Х	X ¹			X ^{4,5}	
Blinded Evaluator Assessments						
Galderma Jawline Scale	Х	X^1		Х	X ⁵	
Subject Assessments						
GAIS				Х	X ⁵	Х
CCI						

CONFIDENTIAL

Effective

Print date: 2022-10-27 21:48

	GALDERMA	Title 05DF2209, Clinical Study Protocol R Lyft Jawline CA	Doc id MA-52559		
¹ Omitted if the screening and basel	ine visits occur on Day 1. Scree	ning visit and baseline visit can be combined if no drug washout is needed	AE = Adverse event		
² For females of childbearing potent	ial		EOS = End of Study		
³ Visit is scheduled only if optional treatment has been performed		GAIS = Global Aesthe	tic Improvement		
⁴ Omitted if optional treatment is not performed		Scale			
⁵ Prior to treatment			Tx = Treatment	Tx = Treatment	

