2.2 Appropriateness of measurements

The effectiveness of *Restylane Lyft Lidocaine* for jawline definition will be evaluated by demonstrating superiority in responder rates (defined as at least 1 grade improvement from baseline on both jawlines concurrently on the GJS) relative to No Treatment group.

The GJS is a 5-point scale for assessment of jawline (see Section 6.3). Each score in the GJS is exemplified by Photographic images of the scale. The Blinded Evaluator and Treating Investigator will perform live assessment of the subject's left and right jawline separately.

The GJS was developed as a quantitative assessment of the jawline area in clinical trials. For the GJS to be considered a reliable and valid tool for assessing aesthetic improvements, live subjects were rated by an independent panel at two sessions separated at least two weeks apart in order to assess the intra- and inter-rater reliability. Based on the validation results, the GJS was determined to be fit for use in clinical settings to detect changes to treatment by improving the jawline definition as a result of volume correction.

Primary effectiveness of *Restylane Lyft Lidocaine* for jawline definition will be evaluated by comparing the responder rate based on the Blinded Evaluators' live assessment of the GJS at 3 months after last treatment. Secondary effectiveness of *Restylane Lyft Lidocaine* by comparing the responder rates based on the Blinded Evaluator's live assessment using the GJS at 6, 9 and 12 months after last treatment for the Treatment group or after baseline for the No Treatment group.

Secondary effectiveness measurements include GAIS as a widely used and accepted measure within the aesthetic field. Other secondary effectiveness measurements are the validated ^{CCI} as well as the ^{CCI} as well as the ^{CCI} as well as the ^{CCI} as secondary effectiveness are the validated ^{CCI} as well as the ^{CCI} as well as the ^{CCI} as well as the ^{CCI} as secondary effectiveness are the validated ^{CCI} as well as the ^{CCI} as a second the results.

Effectiveness evaluation in dermal filler clinical studies includes a combination of clinician-and subject-reported outcomes. As these are aesthetic devices and elective procedures, the incorporation of the subject perspective is critical to evaluate the study benefits associated with dermal fillers.

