8.2 Visit 2: Baseline (Day 1, Initial Treatment)

The screening visit and baseline visit (Day 1) may be performed on the same day if a subject is deemed eligible by the Treating Investigator.

If screening visit and baseline/Day 1 visit are not performed on the same day, the following procedures should be repeated at the baseline/Day 1 visit:

- Review for changes in medical history and concomitant therapies.
- Re-confirm eligibility criteria.
- Perform UPT for all females of childbearing potential Test result must be negative for the subject to be eligible for study treatment.
- Assess GJS Treating Investigator and Blinded Evaluator (see Section 6.3).

Once the subject is deemed eligible for study participation by the Treating Investigator, the following procedures should be completed:

- Record the subject's self-reported height and weight.
- Obtain pre-treatment photographs of the jawline.
- Randomize the subject to treatment or to no treatment.
- Obtain pre-treatment/baseline responses to the CCI with Lower Face and Jawline.

For subjects randomized to no treatment:

• Schedule Visit 3, 1 month (+7 days) after baseline visit),

For subjects randomized to treatment:

- Subjects will be injected with the study product.
- Record all concomitant medications/procedures used prior, during, or after the injection session.
- Record the number of syringes used and the volume of study product injected per treatment area during the injection session. Record the injection details (i.e., injection method and depth of injection).
- Evaluate for device deficiencies. If deficiencies are noted, complete form as specified in section 7.7.3.
- Evaluate post-injection AEs by Treating Investigator.
- Dispense Subject Diary and instruct subject on Diary completion. Remind the subject to bring the diary to next on-site study visit.
- Schedule the 72 hours (±24 hours) follow-up phone call (Visit 2a).
- Schedule Visit 3, 1 month (+7 days) after the baseline visit (Visit 2).

8.2.1 Visit 2a: Follow up 72-hour (±24 hours) telephone call after initial treatment

Visit conducted for subjects randomized to treatment only.

- Interview subject regarding any concomitant therapies.
- Interview subject regarding any AEs that have occurred since receiving treatment. If AEs are reported, notify the Investigator immediately and determine whether subject should return to the site for an unscheduled visit. The Investigator should assess all reported AEs in a timely manner.

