# **1.3 Effectiveness Assessments**

For all assessments, baseline will be defined as the observation that is closest to but prior to study treatment on Day 1 for the Treatment group and baseline visit for the No Treatment group. Where applicable, change from baseline will be calculated as the value at a given time point minus the baseline value.

One month is defined as 4 weeks in the study.

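### Protocol 8.2 lists the baseline subject questionnaire after randomization, and no visible text requires it to be completed beforehand

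*Protocol*

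**What the plan says.** Protocol 8.2 sets out the Day 1 steps for a subject already found eligible. The lead-in says that "the following procedures should be completed", and four bullets follow before the list splits by arm:

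1. Self-reported height and weight.
2. "Obtain pre-treatment photographs of the jawline"
3. "Randomize the subject to treatment or to no treatment"
4. "Obtain pre-treatment/baseline responses to the CCI with Lower Face and Jawline"

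The instrument's name is redacted in the fourth. After the split, controls have Visit 3 scheduled and treated subjects are injected.

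Timing is visible in three places. Section 8.2 itself calls the responses pre-treatment or baseline. Footnote 1 to Table 1 reads "Prior to any planned treatment". SAP 1.3 defines baseline, for all assessments, as the observation "closest to but prior to study treatment on Day 1 for the Treatment group and baseline visit for the No Treatment group".

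On use of the data, Protocol 9.1 plans to summarize continuous endpoints both as observed values and as change from baseline, and SAP 1.3 defines the change score where it applies. Protocol 2.2 mentions redacted secondary effectiveness measures besides the GAIS, and says that "the incorporation of the subject perspective is critical to evaluate the study benefits associated with dermal fillers".

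**The concern.** Only the evaluator is blinded (Protocol 5.7). The comparator is no treatment (5.1.2), and controls are offered the product only at the 12-month visit (5.4.2). A subject randomized on Day 1 is therefore either about to be injected or sent home with a follow-up appointment. Section 4 describes the population as people who intend to have both jawlines treated, so the allocation is likely to matter to them.

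A self-reported score given after that moment is a post-randomization value. Disappointment in controls or anticipation in treated subjects could move it differently in the two arms. If it is then used as baseline, the shift passes in full into the between-arm difference in change. Lower control baselines would hide benefit, and lower treated baselines would inflate it, taking a higher score as better. At stake is the credibility of one subject-reported measure in a study that gives weight to the subject's view.

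**Working it through.** No figure in the plan bears on the order of steps, so the main check is textual. The arithmetic below is illustrative only.

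**Order of the Day 1 steps**

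| Baseline measure | Place relative to randomization |
|---|---|
| Blinded Evaluator GJS | Before (at screening, repeated on Day 1 only if the visits fall on different days) |
| Photographs | Before (second bullet; randomization is third) |
| Subject questionnaire | After (fourth bullet) |

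**Does a visible timing condition prevent late collection?**

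- Section 8.2's own label is tied to treatment. A response given after randomization but before injection meets it.
- Footnote 1 to Table 1 is also tied to treatment. The table attaches it to the randomization row too, so it cannot rank the questionnaire against randomization.
- SAP 1.3 requires a value before treatment in one arm and at the baseline visit in the other. A post-randomization response qualifies in both.
- The questionnaire rows of Tables 1 and 2 are redacted. Table 2's seven footnotes are readable, as are footnotes 1 to 8 of Table 1, and none places an assessment before randomization.

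**Illustration of size**

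Inputs: 105 and 35 subjects (Protocol 9.10, SAP 2.7.1). The shift d and the baseline-to-follow-up correlation r are assumptions; the documents give neither.

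Standard error of a difference in mean change, in SD of change:

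√(1/105 + 1/35) = √0.0381 = 0.195

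- d = 0.1: 0.1/0.195 = 0.51 standard errors
- d = 0.2: 0.2/0.195 = 1.02 standard errors

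With 94 and 31 subjects after 10% dropout, √(1/94 + 1/31) = 0.207, and the same shifts are 0.48 and 0.97 standard errors.

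Now put d in SD of the score, with equal SD at both times. The SD of change is √(2(1 − r)), which equals 1 at r = 0.5. If there is no true effect, the chance that a two-sided 5% comparison of change scores excludes zero is 1 − Φ(1.96 − d/SE) + Φ(−1.96 − d/SE), where SE = √(2(1 − r)) × 0.195:

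| d | r = 0.3 | r = 0.5 | r = 0.7 |
|---|---|---|---|
| 0.1 | 7% | 8% | 10% |
| 0.2 | 14% | 18% | 26% |
| 0.3 | 26% | 34% | 51% |

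Adjusting for baseline reduces the bias to r × d but does not remove it. At r = 0.5 and d = 0.2 the bias is 0.1 SD, its standard error is √(1 − 0.25) × 0.195 = 0.169, and the chance is 9%.

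**The case against.** The strongest reply is that a bulleted list is not a sequence. The lead-in sets no order, and the protocol's bullets do not always follow one: the pregnancy test precedes the Treating Investigator's GJS at touch-up (8.3), while the two are reversed at the optional treatment (8.5). Where order matters, the protocol usually says so. This stands in part. A reader might infer that the questionnaire definitely is collected after randomization; the text does not support that. It lists this order and permits it. Still, the list otherwise runs chronologically from eligibility to injection, so a site would naturally follow it.

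The second reply is redaction. The instrument's name, its schedule rows and its SAP analysis are hidden, and hidden text may set the order or may not use change from baseline at all. This also stands. What is hidden cannot be called missing, and the use of change scores rests on the general rule in 9.1. The readable footnotes make a hidden safeguard in the schedules less likely, but do not exclude one.

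The third reply is reach. A reader might infer that the trial's main result, or the subject's view as a whole, is compromised. The documents do not support that. The primary endpoint is the Blinded Evaluator's GJS. The subject GAIS is rated against photographs that are listed before randomization. P-values for non-primary endpoints serve interpretation only (9.4). Subjects also know their arm at every follow-up response, so re-ordering removes only one part of the expectation bias.

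**Conclusion.** The point holds in limited form, at low severity. As listed, the questionnaire follows randomization, and nothing visible requires the reverse. A site working down the list would obtain a baseline from subjects who very likely know their allocation, which leaves any between-arm comparison of change on this instrument open to bias of unknown size and direction.

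This rests on three inferences: that sites follow the bullet order; that subjects learn their arm at randomization, which the design implies but the protocol does not state; and that the general change-from-baseline rule reaches this instrument. The half to one standard error given above is a scale for assumed shifts of 0.1 to 0.2 SD, not an estimate. A descriptive label limits the claims made from the result, but it does not remove bias from a reported difference.

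**What to change.** - Protocol 8.2: move the questionnaire bullet above the randomization bullet, and state that all baseline subject assessments are completed before randomization.
- SAP 1.3: define baseline for subject-reported measures as the last value before randomization in both arms.

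Both changes apply unless redacted text already says this, which the sponsor can check at once.

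The cost is a minor protocol amendment with REB approval (Protocol 10.7.1) and one line of SAP text, handled as an SAP amendment if the SAP is final (SAP 2.1). Visits, instruments, sample size and power do not change. For any responses already collected after randomization, the observed follow-up values that 9.1 also plans should be shown beside the change scores, since they do not depend on the baseline response.

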9. STATISTICAL DESIGN AND ANALYSIS

9.1 General

A Statistical Analysis Plan (SAP) with a description of all statistical analyses will be developed.

All study data will be listed in subject data listings. All statistical analyses, including summary tables and data listings, will be performed using SAS. Confidence intervals will be two-sided and constructed at a confidence level of 95%.

All endpoints will be summarized descriptively. Continuous endpoints will be summarized using mean, median, standard deviation (SD), minimum and maximum values, for the observed value as well as the change from baseline. Categorical endpoints will be presented in frequency tables with number and percentage of observations for each level.

9.2 Analysis populations

The following populations will be defined:

Safety population:

Includes all subjects who were treated with *Restylane Lyft Lidocaine*. Subjects are analyzed based on the as treated principle (i.e., according to the treatment actually received).

Intention-to-treat (ITT) population:

Includes all subjects who were randomized based on the as randomized principle (i.e. according to the treatment they were randomized to).

Per protocol (PP) population:

Includes all subjects in the ITT who complete the visit 4 after baseline without any deviations considered to have substantial impact on the primary effectiveness outcome.

The ITT is the primary population for all effectiveness analyses. The primary effectiveness analysis will be repeated using the PP analysis set if there is at least a 10% difference in the number of subjects between the PP and ITT sets. Safety analysis is performed based on the safety population. The disposition of subjects will be presented in tables and/or figures as appropriate.

9.3 Demographics, baseline assessments, and subject characteristics

Demographic endpoints, baseline assessments, and subject characteristics will be presented by treatment group, based on the ITT analysis set using descriptive statistics, as appropriate.

9.4 Effectiveness analysis

Continuous endpoints will be summarized using descriptive statistics, e.g., mean, median, SD, minimum and maximum values. Categorical endpoints will be presented in frequency tables with number and percentage of observations for each level.

Responder rate regarding GJS and GAIS will be presented together with a 95% confidence interval (based on the binomial distribution). The difference in responder rate regarding GJS and GAIS will be calculated between the two groups presented together with a 95% confidence interval.

For the primary effectiveness analysis, a responder will be defined as a subject with at least 1 point improvement from baseline based on the GJS. For a significant result, the two-tailed p-value of the comparison of responder rates between the treated and untreated subjects at 3 months using the Fisher's exact test needs to be smaller than 0.05.

No adjustment to the level of significance will be performed; p-values obtained for any endpoint other than the primary will only be provided for ease of interpretation of the results.

Secondary analyses will include analysis of responders at each visit. Robustness of the results of the primary endpoint and adverse events analysis will be investigated across the PP population. All formal statistical testing will be performed at a significance level of 5% (2-sided).

9.5 Safety analysis

The number and percentage of subjects reporting each pre-defined, expected, post-treatment symptom, as collected in the 28-day diary, will be presented in total and by maximum intensity. Number of days with the event will be presented.

All AEs will be coded according to medical dictionary for regulatory activities (MedDRA) and summarized by system organ class (SOC), preferred term (PT) and treatment. AEs related to the study device or injection procedure and unrelated AEs will be presented by maximum intensity, SOC and PT. For related AEs, the number of days to onset and the duration of the event will be summarized by SOC and PT using mean, SD, min, max and median. Action taken for related AEs will also be summarized by SOC and PT. Serious AEs will be listed.

In addition, a summary of all AEs will be provided, which will include (but is not limited to):

Page 51 of 67

Version: 1.0

GALDERMA

Doc id

- number of subjects with at least one AE and number of events (in total as well as SAEs)
- number of subjects with at least one related AE and number of events (in total as well as SAEs)
- number of subjects with at least one un-related AE and number of events (in total as well as SAEs)
- number of subjects who did not have an AE

9.6 Handling of missing data

The number of missing values will be summarized and reported as appropriate. For the ITT analysis of the Treating Investigator GJS Responder rate at Month 3 after last treatment for Treatment group (primary endpoint), missing values will be assumed to be missing due to lack of effect. Therefore, the primary method of imputation will use the baseline observation carried forward (BOCF) method.

Impact of missing data on the primary endpoint will be evaluated by performing sensitivity analysis based on the observed cases, as well as worst-case and best-case imputation in the ITT set.

All other effectiveness endpoints will be evaluated based on the observed cases in ITT.

Descriptive statistics of all safety data will be performed on observed cases in the Safety population

9.7 Interim analysis

No formal interim analysis will be performed. However, analysis of data could take place at a time point after the last collection of primary endpoint data. This will not affect the conduct of the study, and none involved in the study will have access to this data. The SAP will be final and signed before this data cut.

9.8 Independent data monitoring committee

Not applicable to this study.

9.9 Withdrawals and deviations

All withdrawn subjects will be listed individually, including at least subject number, date and reason for withdrawal, and last visit performed.

Subjects with CSP deviations will be listed individually, including subject number, and observed deviation. Depending on the seriousness of the deviation, the subject may be excluded from the PP population, which shall be documented prior to database lock (DBL).

Deviations from the statistical plan will be documented in the Clinical Study Report (CSR). If the statistical plan needs to be changed before DBL, but after the finalization of the SAP, the SAP will be amended.

9.10 Sample size

A total sample size of approximately 140 subjects will be included in this study. For the responder rate in GJS, a Fisher's exact test using a 5% two-sided significance level will have approximately 90% power to demonstrate difference between a responder rate of 70% in the *Restylane Lyft Lidocaine* group, and a responder rate of 35% in the no treatment control group when the sample

sizes are 105 and 35, respectively. Accounting for 10% dropouts, approximately 140 subjects need to be randomized in a 3:1 ratio.

10. ETHICS AND GENERAL CLINICAL STUDY CONDUCT

10.1 Ethical considerations

10.1.1 Statement of ethical compliance

The study shall be conducted in compliance with the CTA, the Clinical Study Protocol (CSP), GCP, and applicable regional and national regulations. The study shall be conducted in accordance with the ethical principles that have their origin in the Declaration of Helsinki (1964, and its amendments in force at the initiation of the study).

The study shall follow the international standard for clinical study of medical devices for human subjects, ISO 14155:2020.

The study related medical care provided to the subjects during the study is the responsibility of an appropriately qualified medical doctor (i.e., the PI) or, where appropriate any other person entitled by national law to provide the relevant patient care.

10.1.2 Application to research ethics board and/or regulatory authorities

It is the responsibility of the Principal Investigator (PI) to obtain approval of the CSP/CSP amendment(s) from the REB The study shall not begin until the required favorable opinion from the REB has been obtained. The PI shall file all correspondence with the REB in the Investigator file and copies of REB approvals shall be forwarded to the Sponsor. Any additional requirements imposed by the REB or regulatory authorities (RA), shall be followed.

The study does not require application for approval from the RA as it is a post approval phase IV study. The collection, access to, processing, and transfer of protected health information or sensitive personal data shall be carried out in accordance with applicable rules and regulations.

